$$Y_{ict13} = \beta_0 + \beta_1 D_c + \beta_{2:4} A_c' + \beta_5 Y_{ict0} + \beta_{6:9} I_i' + \beta_{10:k+10} X_i' + \epsilon_c$$

Where:

- D_c is a binary treatment variable for all participant groups to conserve power. Where treatment = 0 if they are in the comparator group and treatment = 1 if:
 - the social worker or family support worker is a member of a team assigned to treatment,
 - foster carer cares for a child or young person who case is held by a social worker who is a member of a team assigned to the intervention group, or
 - the child or young person's case is held by a social worker in a team assigned to the intervention group.
- I'_i is a vector of interaction terms between treatment (again binarised) and the categories of the most recent type of CSC intervention (coded as Child in Need, Child Protection Plan, or Looked After - LA fostering / kinship care, Looked After - IFA / other LA fostering / other placement type, or missing; with Child in Need as the reference category).
- X'_i is a vector of covariates including the most recent type of CSC intervention.
- All other variables are the same as the regression specification (depending on the outcome under consideration) outlined under the "Primary and Secondary Analysis" section.

We interpret the coefficient on each interaction term as the differential impact of Kitbags on each cohort in comparison with CYP with a CINP. Whether there is a differential impact by CSC involvement may be related to a few factors: whether Kitbags are more helpful for a particular cohort, whether Kitbags are used differently with different cohorts or whether Kitbags are used at different frequencies with different cohorts. This trial of Kitbags where social workers use Kitbags on their visits is the intervention developer's current best guess about the way that social workers would use Kitbags if the programme were to be rolled out more generally. Given this, it isn't necessarily problematic that the coefficient estimates on the interaction terms encompass these reasons why the treatment may be different for different cohorts. However, it is helpful for the future development of the intervention to try to pick apart these.

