Although the statutory requirements are different, in practice the frequency of visits is similar for children with a CINP and children with a CPP and so the coefficient on the treatment x CPP interaction is likely to represent the impact on the different cohorts and how it's used (rather than the frequency).

Foster carers and kinship carers in the intervention group also receive a Kitbag. This means that children and young people in foster care placements or placed with kinship carers will likely use the Kitbag more frequently than children and young people fostered by foster carers employed by independent fostering agencies or other local authorities - they may use it with their social worker and their foster / kinship carer. The coefficient on the treatment x Looked After - IFA / other LA fostering / other placement type is thus perhaps a better indication of the impact of Kitbags on CYP who are looked after than the coefficient on the treatment x Looked After - LA fostering / kinship care group (although there will be different selection mechanisms into foster / kinship care and the IFA / other LA / other placements).

We will try to understand how Kitbags are used with the different cohorts in the implementation and process evaluation.

To give some indication of the additional treatment effect of the Kitbag being used with the CYP by the foster carer or kinship carer, we change the reference category to Looked After - IFA / other LA fostering / other placement type. We interpret the coefficient on the Looked After - LA fostering / kinship care category interacted with treatment as indicative of the additional treatment effect of the Kitbag being used with the CYP by the foster carer or kinship carer. However, this analysis is non-causal as there may be different selection into placement type.

Impact on CYP by age

Additionally, we will conduct analysis looking at whether there is a differential impact for young people by age (age category at the beginning of the trial). We add an interaction term of treatment and age category at the start of the intervention period:

$$Y_{ict13} = \beta_0 + \beta_1 D_c + \beta_{2:4} A_c' + \beta_5 Y_{ict0} + \beta_{6:8} I'_i + \beta_{9:k+9} X'_i + \epsilon_c$$

Where:

- D_c is a binary treatment variable for all participant groups to conserve power. Where treatment = 0 if they are in the comparator group and treatment = 1 if:

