 - the social worker or family support worker is a member of a team assigned to the intervention group,
 - foster carer cares for a child or young person who case is held by a social worker who is a member of a team assigned to the intervention group, or
 - the child or young person's case is held by a social worker in a team assigned to the intervention group.
- I'_i is a vector of interaction terms between the treatment (binarised) and age group (4-11, 11-17, 18 years, or missing with 4-11 as the reference category)
- All other variables are the same as the regression specification outlined under the "Primary and Secondary Analysis" section.

These are exploratory because the analysis was not designed to be sufficiently powered for subgroup analysis.

Contextual Factors Analysis

Where caseloads are high and complex, we would expect that there is less time for direct work. Ideally, we would be able to track the caseload and complexity of each social worker but caseload numbers may have different definitions in each local authority and case complexity is not routinely recorded. We thus ask social workers' for their subjective judgement of their caseload and case complexity over the last year in the social worker survey at T13. We multiply the responses to these two questions to get a proxy for workload (a continuous variable).

We add an interaction term of treatment and workload:

$$Y_{ict13} = \beta_0 + \beta_1 D_c + \beta_{2:4} A_c' + \beta_5 Y_{ict0} + \beta_6 I_i + \beta_{7:k+7} X'_i + \epsilon_c$$

Where:

- D_c is a binary treatment variable for all participant groups to conserve power. Where treatment = 0 if they are in the comparator group and treatment = 1 if:
 - the social worker or family support worker is a member of a team assigned to the intervention group,
 - foster carer cares for a child or young person who case is held by a social worker who is a member of a team assigned to the intervention group, or
 - the child or young person's case is held by a social worker in a team assigned to the intervention group.
- I_i is an interaction term between the treatment (binarised) and workload
- All other variables are the same as the regression specification outlined under the "Primary and Secondary Analysis" section.

Missing data strategy

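### The interaction for looked-after children in agency or other placements is a difference from Child in Need children, but one sentence offers it as the impact on looked-after children

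*Protocol*

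**What the plan says.** The point lies in the protocol, Exploratory Analysis, under the heading on impact by level of CSC involvement. The model there has a binary treatment term, local authority effects, the earlier outcome, covariates and a set of interactions:

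- Interactions: "I'_i is a vector of interaction terms between treatment (again binarised) and the categories of the most recent type of CSC intervention".
- Reference: the categories end with "or missing; with Child in Need as the reference category".
- Status main effects are in the model: "X'_i is a vector of covariates including the most recent type of CSC intervention".
- Stated meaning: "We interpret the coefficient on each interaction term as the differential impact of Kitbags on each cohort in comparison with CYP with a CINP".

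The text then discusses individual coefficients. Children in local authority foster or kinship placements may use a Kitbag with their carer as well as with their social worker. For that reason the interaction for looked-after children in agency or other placements (IFA/other below) "is thus perhaps a better indication of the impact of Kitbags on CYP who are looked after than the coefficient on" the local authority fostering and kinship interaction. Finally, to isolate the extra effect of carer use, "we change the reference category to Looked After - IFA / other LA fostering / other placement type".

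The section does not say that the main treatment coefficient must be added to an interaction to obtain the effect in a group. Nor does it say how to read the main coefficient after the reference category is changed.

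**The concern.** The same coefficient is given two meanings. By definition it is the effect in IFA/other children minus the effect in Child in Need children. In the later sentence it indicates the impact on looked-after children, with no comparator named. An analyst who follows the later sentence could make a statement about children in care that is wrong in size and possibly in sign. The standard error attached would be that of a difference, not of the group's own effect. In Table 1 the CIN/CPP teams and the CLA teams are listed as separate teams, so such a difference carries sampling error from both sets.

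The subgroup statement matters to the authors. The Randomisation section gives priority to balance on team type so that the programme's impact can be compared across these subgroups.

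**Working it through.** **Algebra of the stated model.** Write b1 for the treatment coefficient and b_g for the interaction of treatment with status group g. Because Child in Need is the reference and the status main effects are included:

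- effect in Child in Need = b1
- effect in group g = b1 + b_g
- so b_g = (effect in g) − (effect in Child in Need)

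Thus b_g equals the effect in g only when b1 = 0.

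**Illustration.** For both child outcomes a lower value is better, so benefit is negative. The 0.127 SD is the MDES in the sample-size table, borrowed here only as a convenient size. The 0.06 SD and the pairings are assumptions, because the protocol gives no subgroup effects.

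| Effect in Child in Need | Effect in IFA/other | Interaction b_g | Literal reading as an impact |
|---|---|---|---|
| −0.127 | −0.127 | −0.127 − (−0.127) = 0 | none, although the benefit is 0.127 |
| −0.127 | −0.06 | −0.06 − (−0.127) = +0.067 | harm, although the benefit is 0.06 |
| −0.06 | −0.127 | −0.127 − (−0.06) = −0.067 | benefit of 0.067, although it is 0.127 |
| 0 | −0.06 | −0.06 − 0 = −0.06 | correct |

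**Simulation check.** 300 simulated trials used 60 teams of 150 children and ICC 0.03, all from the sample-size table. Assumed shares were Child in Need 45%, CPP 20%, local authority fostering/kinship 20% and IFA/other 15%. The shares do not change the expected coefficients. The model was OLS with treatment, status and their interactions. Mean estimates in SD units:

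| True effects | b1 | IFA/other interaction | b1 + interaction, IFA/other |
|---|---|---|---|
| −0.20 in every group | −0.198 | −0.003 | −0.202 |
| −0.20 in Child in Need, −0.10 elsewhere | −0.200 | +0.097 | −0.103 |
| 0 in Child in Need and CPP, −0.30 in fostering/kinship, −0.20 in IFA/other | −0.003 | −0.192 | −0.195 |

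The sum recovers the true effect in each case. The interaction alone does so only in the third, where the Child in Need effect is zero. The simulation concerns point estimates only.

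**The planned refit.** With IFA/other as reference, the main treatment coefficient becomes the effect in IFA/other children. The fostering/kinship interaction becomes the effect in fostering/kinship minus the effect in IFA/other. The protocol uses only that interaction, and reads it correctly as an additional effect.

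**The case against.** The strongest defence is that the governing rule is stated correctly just before, and nothing withdraws it. The disputed sentence is comparative and hedged. Its subject is which of two looked-after coefficients is less mixed with carer use of the Kitbag. Both omit the same b1, so the ranking is the same for interactions and for sums, and impact may be shorthand for differential impact. The refit already produces the effect in IFA/other children. The analysis is also labelled exploratory: "These are exploratory because the analysis was not designed to be sufficiently powered for subgroup analysis".

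Much of this stands, and it limits the weight of the point. It does not remove it. The hedge concerns which coefficient to prefer, not whether either one is an impact. Where the authors mean a difference, in the refit, they say so. The site-effects subsection explains how to read the main treatment coefficient, but this one does not. The refit is made for another contrast, and its main coefficient is not named as a result to report.

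Two stronger readings are tempting. A reader might infer that the child protection sentence makes the same error, since it says "the coefficient on the treatment x CPP interaction is likely to represent the impact on the different cohorts and how it's used (rather than the" (the sentence closes by naming how often visits take place). It does not. The argument there is that visit frequency is similar in the two groups and so drops out, which works only if the coefficient is a difference from Child in Need children. A reader might also infer that the plan commits the authors to reporting equal benefit as no impact on children in care. No text says so. Under the stated definition, a zero interaction would be reported as no difference from Child in Need children.

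**Conclusion.** The point holds for the looked-after sentence alone, as an inconsistency of interpretation. The model is sound, but a difference is offered as an indication of an effect. If that sentence is followed literally, the error equals the Child in Need effect with its sign reversed. That makes the expected value zero under equal benefit, and gives the wrong sign when the benefit in looked-after children is real but smaller. The algebra needs no assumption beyond the stated model. The figure of 0.067 SD rests on assumed subgroup effects and is not a forecast.

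The consequence is confined to an exploratory, unpowered subgroup analysis. It is still worth correcting before analysis, because the statement concerns children in care and the correction is almost free.

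**What to change.** - For each status group, report b1 + b_g with its team-clustered standard error and confidence interval, and call only that sum the impact on the group. The variance is Var(b1) + Var(b_g) + 2 Cov(b1, b_g), from the team-clustered covariance matrix.
- For IFA/other, this sum equals the main treatment coefficient in the refit already planned. State that it will be reported as such.
- Keep the interaction coefficients as exploratory tests of difference between groups.
- Reword the looked-after sentence so that it compares the group effects (the sums), or says explicitly that it speaks of differences from Child in Need children.

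The cost is one linear-combination command per group and a change to one sentence. Design, data and model stay as they are.

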- for social workers and family support workers: the social worker or family support worker was a member of a team assigned to the intervention at point of randomisation and 0 else;
- for foster / kinship carers: the carer cares for a child or young person whose case is held at the point the foster carer enters the sample, by a social worker who is a member of a team assigned to the intervention at point of randomisation and 0 otherwise.

Although there is some turnover of social workers, family support workers and foster carers, about 80% of those at T0 (April 2021) will still be working with the local authority at T13 (May 2022), and so 80% will have received the full 12 months of the intervention. Binarising the treatment seems a reasonable proxy in this case.

For the outcomes relating to children, treatment is coded as a binary variable. When children enter the sample, at either the point of randomisation, or the point they become eligible (e.g. their case opens and meets other criteria) they will be allocated to treatment if the team of their allocated social worker was randomised to treatment.

Covariates

Including control variables increases the precision of the estimate. In each regression, we control for a number of relevant covariates. We outline different categories of covariates below.

Site effects

We include site fixed effects but not site-treatment interaction terms.

Previous outcome measures

We control for the previous measurements of the outcome variable where data is available. For the survey-based measures for social workers, family support workers and foster carers, the same measures will be asked at T6 (October 2021) and T13 (May 2022), and for administrative data we expect previous values to be available. For the outcomes of the CYP and parents / carers (including kinship carers), the previous measure of the outcome will be at T0 (April 2021) or when they entered services if they entered services after T0 (April 2021).

Other covariates

For CYP outcomes (primary outcome i) and secondary outcome i)), we include the following vector of individual-level covariates:

- gender (coded as male, female, or other/missing)
- age group (4-11, 12-17, 18 years, or missing with 4-11 as the reference category)
- ethnicity (Asian / Asian British, Black / African / Caribbean / Black British, Mixed / Multiple ethnic groups, Other ethnic group, White, missing; with the majority group as the reference category)

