Missing post-intervention data is a risk for this trial as some of the secondary outcomes are collected via primary data collection (an online survey) and the attrition is likely to be high given that the follow-up period is over a relatively long period of time (4 months - 12 months later) and the professionals may have left their employer.

Covariates

- If the covariate has more than 30% of the data missing, we will drop the covariate.
- For each covariate in the main model (see the “Covariates” section) that has up to 30% of the data missing, we will regress an indicator of missingness on the other covariates in the main model and outcomes using logistic regression, clustering the standard errors at the team level. If any of the coefficients on the covariates of the missingness model are statistically significant at the 5% level, then data is not missing completely at random (MCAR).
- To distinguish between whether the data is missing at random (MAR) i.e. missing conditional on observables or missing not at random (MNAR) i.e. missing conditional on unobserved variables, for all the covariates that were not MCAR we then impute the missing values of the covariate of interest (using a missing category for categorical variables and multiple imputation for numeric variables) and compare the treatment estimates using the imputed data and data restricted to the complete cases. If the results are similar (i.e. significant / insignificant, the same direction and only differing in magnitude of up to 20%), then data is likely to be missing at random (MAR). If the results are dissimilar, the data is likely to be missing not at random (MNAR).

If the data on covariates are MCAR or MAR, then complete case analysis is likely to be unbiased but less well powered. To maintain power we use a missing category for categorical variables as missingness is likely to be a predictor in itself and multiply impute missing numerical covariates (including pre outcome measures). We ignore the clustered structure of the data because cluster sizes are small, cluster follow-up rates may be highly variable and we expect the ICC to be low (we assume the ICC to be 0.03 in power calculations)²¹.

Outcomes

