Focus groups	T10-T12	
We will send information about the focus groups to the practitioners via the Kitbag super lead and then purposively sample aiming for a heterogenous sample of practitioners from different team types and of different roles.
 
For the focus group discussions for the super leads, all will be invited to attend.

Interviews (n=16)	T10-T12	
Children: Practitioners who attend the focus group discussion will be asked to identify children on their caseload who may be open to participating.
 
Foster carers: the Kitbag leads in the fostering teams will be asked to send information about the interviews to the foster carers. We

		will purposively sample aiming for a heterogenous sample of foster carers of children of different ages.
Survey (assume 10% response rate)	T1 T13	A survey will be shared with all staff (i.e. no sampling) across intervention and comparator teams: 
 • Social workers and family support workers (includes Kitbag Leads) • Inhouse foster carers (the survey will be adapted slightly for this group) • Team Managers
Observations of workshops (n=4)	T3-T4	A researcher or research assistant will observe at least one workshop per local authority.

Analysis

Qualitative data preparation and analysis of interview and observational data

Interviews will be recorded, transcribed and pseudonymised prior to analysis. Qualitative analysis of interview and observational data will use NVivo software and follow a thematic analysis approach. This will involve data familiarisation, checking accuracy of transcription, labelling the data with descriptive codes and developing themes which describe patterns across the data to answer the pre-specified research questions. Analysis will look for patterns, consistencies and inconsistencies across different informants and time points that might be informative for the research questions.

The following steps will be taken to ensure rigor in the analysis and reporting of qualitative data:

- Confidence that the findings are an accurate reflection of participant experience will be ensured through presentation of examples of participant responses using quotes, and triangulation between different informants and data collection methods.
- The degree to which findings are transferable to other contexts will be considered through detailed description of contextual factors, and collection of data from a range of informants to gather a range of perspectives.

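### The workload moderator exists only for staff who answer the T13 survey (assumed response 10%), so for outcomes from other sources the interaction would rest on a small, self-selected subset rated after treatment

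*Protocol*

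**What the plan says.** Caseload (quantity and complexity) is the only contextual factor on the protocol's front page. In *Contextual Factors Analysis*, workload is the product of two self-report items, staff's "subjective judgement of their caseload and case complexity over the last year in the social worker survey at T13". The reason given for not using routine data is that "caseload numbers may have different definitions in each local authority and case complexity is not routinely recorded". No fallback is given for staff who do not answer.

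The model adds one term: "I_i is an interaction term between the treatment (binarised) and workload". Its scope is worded broadly: "D_c is a binary treatment variable for all participant groups to conserve power", followed by definitions for staff, foster carers and children.

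Under *Data collection schedule*, the survey row reads "Survey (assume 10% response rate" and adds: "A survey will be shared with all staff (i.e. no sampling) across intervention and comparator teams". No other response rate is stated for this survey. On turnover, the *Analysis plan* expects that "about 80% of those at T0 (April 2021) will still be working with the local authority at T13". Under *Missing data strategy*, *Covariates*, the first rule is: "If the covariate has more than 30% of the data missing, we will drop the covariate". The diagnostic and imputation steps that follow are set out for main-model covariates with up to 30% missing.

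**The concern.** A moderator is usable only where it is observed. Children's social care involvement, the SDQ and days attended come from administrative data covering nearly everyone, and carer self-efficacy comes from the carers' own survey. If workload is known only for the few staff who answer at T13, the interaction for these outcomes discards most of the sample and keeps those whose worker chose to reply.

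Timing adds to this. Workload is rated after a year of exposure, so treatment may affect both who answers and what they report. At stake is whether the trial can say anything about its one named contextual factor.

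**Working it through.** **Inputs.** Response 10% (*Data collection schedule*). Retention 80% (*Analysis plan*). 60 teams of 6 to 8 social workers (*Design*; Table 1). 300 intervention staff (Table 2), so about 600 in both arms if control is similar (assumption). Upper staff figure c.1000 (*Data protection*). 9,000 to 9,300 children (MDES table; *Participants*). ICC 0.03, R² 0.8 (child) and 0.1 (team, 3 covariates), 150 children per team, half the teams treated (*Sample size*).

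**1. The plan's own figure.** There is none for the workload analysis, so the main-effect MDES of 0.127 is the yardstick. With 4 blocks, df = 60 − 2×4 − 3 = 49:

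MDES = (t₀.₉₇₅ + t₀.₈₀) × √[0.03×0.9/(0.25×60) + 0.97×0.2/(0.25×60×150)] = 0.124.

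This is within 3% of the stated 0.127.

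**2. Missing share.** 1 − 0.10 = 90% of staff have no score, three times 30%. Keeping missingness at 30% needs 70% response. If the denominator is T0 staff, that is 0.70/0.80 = 87.5% of those still in post.

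**3. Respondents and empty teams** (equal team sizes and independent response assumed; chance of no respondent = 0.9^(staff per team)):

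| Staff | Respondents | Per team | Teams with none |
|---|---|---|---|
| 360 | 36 | 0.6 | 53% (32 of 60) |
| 480 | 48 | 0.8 | 43% (26) |
| 600 | 60 | 1.0 | 35% (21) |
| 1000 | 100 | 1.7 | 17% (10) |

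**4. Children.** With equal caseloads and one worker per child, 10% of 9,000 to 9,300 is 900 to 930 scored and 8,100 to 8,370 unscored. Putting about 900 children into the formula in step 1 gives a *main-effect* MDES of 0.147 if all 60 teams stay in (15 children each). It is 0.158 to 0.204 if only the 50 down to 28 teams with a respondent remain. The comparison is 0.124 on the full sample. ICC and R² are held fixed and clustering by worker is ignored. The interaction would be less precise than the main effect.

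**5. Days attended and carers.** Days attended was chosen so that leavers stay in the analysis. A T13-only moderator removes them again: about 20% of T0 staff cannot have a score at any response rate. For carers, both the carer and the child's worker must answer. If 10% applies to each and the two are independent, 0.10 × 0.10 = 1% of invited carers have both values.

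**6. Staff self-efficacy and stress.** Outcome and moderator come from the same T13 survey, so workload adds little missingness among analysed respondents. Numbers are still small. The detectable interaction per SD of workload is roughly (t₀.₉₇₅ + t₀.₈₀) × √(4/r), with df = r − 10 and clustering ignored: 0.57 SD for r = 100 and 0.97 SD for r = 36.

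**7. Timing.** The other moderators of children's effects, type of social care involvement and age group, are fixed at the start. Workload alone is rated at the end. Lower stress is a hypothesised effect, and the stress scale includes items such as demanding, pressured and overwhelming, close in content to a subjective workload rating.

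**The case against.** Several points on the other side stand.

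- A reader might infer that the analysis cannot be run at all. The documents do not support that. For staff self-efficacy and stress the shared survey means little extra missingness, and the protocol already acknowledges survey attrition. A complete-case model could also be fitted elsewhere, on a small subset.
- A reader might infer that the 30% rule deletes the term. The rule is written for covariates, and workload is not in the *Covariates* list. Applying it to a moderator is a reading, although no other rule is given.
- A reader might infer that the plan itself expects Kitbag to change perceived workload. It hypothesises effects on self-efficacy, stress and absence, not on ratings of caseload or complexity. Influence on the rating is plausible but is an inference.
- The 10% is a planning figure in the process-evaluation schedule, in a row that lists T1 and T13 where the *Survey* section has T6 and T10–T13. Replacements for leavers may also answer. The realised rate may differ, but nothing in the protocol points to one near 70%.
- The wording on participant groups repeats that of the age analysis, so it does not settle scope. The equation omits the team-characteristics term, as the child-outcome model does, so child outcomes are probably intended.
- How a child acquires a worker's score is undefined here. A statistical analysis plan could supply it, so that gap is not counted against the protocol.

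**Conclusion.** The concern holds for outcomes not taken from the staff survey: children's social care involvement, SDQ, days attended and carer self-efficacy. At the stated 10% response most records have no workload value. The figure is about 90% for children, given equal caseloads and a single child–worker link. The interaction would be estimated in a self-selected subset using a post-treatment rating or, if the 30% rule is read to cover moderators, dropped. For staff self-efficacy and stress the weakness is small numbers, selective response and post-treatment rating.

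This is a subsidiary analysis, placed after subgroup analyses that the protocol calls exploratory. It would be wrong to infer that the primary or any secondary treatment estimate is affected. It is worth correcting because a baseline alternative is cheap.

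**What to change.** For outcomes outside the staff survey, define the moderator as T0 team-level caseload: open children per team worker, counted by one common rule from the child-level administrative extract and standardised within local authority. Assign it by the team at sample entry, matching the treatment coding. A common counting rule answers the protocol's objection about differing local definitions.

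Keep the T13 survey score as a supplementary, explicitly exploratory moderator for staff self-efficacy and stress. State whether the 30% rule applies to moderators.

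The cost is small. Child-to-team allocation is already needed to assign treatment and cluster standard errors, T0 team size is a listed covariate, and the cost evaluation already needs the opening caseload of treated teams. The same count is needed for control teams. A worker-level T0 count is not a safe substitute: staff who join later have none, and child–worker linkage is not assured. The downside is that case complexity, half of the named contextual factor, and within-team variation in caseload are not captured.
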